**Table 14. PK Sampling Expansion**

Treatment Cycle 1 cycle = 3 weeks		Cycle 1 - 4		Cycle 5  - PD	End of Treatment	Safety Follow-up	Unscheduled
1Q3W	Visit	1		1	-	-	1-X
	Day	1d				30 days after last dosing	
Before Infusion [on infusion days]		X	X	X	X	X	X 
End of infusion (+15 minutes) 		X					

Treatment Cycle 1 cycle = 4 weeks		Cycle 1 - 4				Cycle 5  - PD	End of Treatment	Safety Follow-up	Unscheduled
3Q4W	Visit	1	2	3	4 	1	-	-	1-X
	Day	1d	8d	15d	22d	1d		30 days after last dosing	
Before Infusion [on infusion days]		X	X	X	X	X	X	X	X 
End of infusion (+15 minutes) 		X	X	X		X			

 Allowed time windows are indicated in parentheses.

 Optional.

[figure not shown]
 Every 4th cycle.

 For Cycle 1 and 2 only

### 8.3 Exploratory Biomarker Analyses

[figure not shown]
**Table 15.**

Document Name: GCT1021-01 Protocol

Document Number: TMF-03326

Version: 11.0

Document Name: GCT1021-01 Protocol

Document Number: TMF-03326

Version: 11.0

---

**Table 16.**

Document Name: GCT1021-01 Protocol

Document Number: TMF-03326

Version: 11.0

---

## 8.4 Clinical Assessments

### As of Amendment 10:

- Height, weight, and physical examination outcome are no longer to be recorded in the eCRF.
- ECGs will be taken locally.
  - Any irregularity observed or occurring during the ECGs should either induce a repeat of the ECG or be annotated in the medical journal.
  - New or worsened clinically significant abnormalities should be recorded as AEs on the AE form.
- Post-baseline CT-scans are to be performed every 12 weeks ( $\pm 7$  days) and are not to be sent for central reading.
- Vital signs should be measured if deemed necessary by the investigator, but are not to be recorded in the eCRF.
- Any medication or therapy other than enapotamab vedotin that is related to an AE or is considered prophylactic treatment is considered concomitant medication.
- Patient diary data are not to be recorded in the eCRF.

Refer to [Appendix VI, Table 31](#) and [Section 16.2](#) for applicable clinical assessments as of Amendment 10.

### 8.4.1 Demographics

Date of birth, race, ethnic origin, gender and smoking and drinking habits will be recorded at screening in the eCRF.

### 8.4.2 Disease Status

Primary site of cancer and initial and current disease stage [Tumor Nodes Metastasis (TNM) staging system] will be recorded at screening in the eCRF.

For patients with NSCLC, the patients' mutational tumor status with respect to EGFR mutations and ALK rearrangement and for patients with melanoma with respect to BRAF and NRAS mutations will be also recorded (incl. date of the assessment). In addition, for patients with NSCLC who have previously been treated with PD-1 or PD-L1 inhibitors, the PD-L1 expression level at the time of initiation of prior PD-1/PD-L1 inhibitor treatment will be recorded.

Document Name: GCT1021-01 Protocol

Document Number: TMF-03326

Version: 11.0

---

#### **8.4.3 Medical History**

Past and all current diseases will be recorded at screening in the eCRF. Non-serious AEs (signs, symptoms and diagnosis) occurring between visit 0 (Screening) and C1V1 should be recorded as medical history.

#### **8.4.4 Height and Weight**

Height (without shoes) must be measured at Visit 0 (Screening) and recorded in the eCRF rounded to nearest centimeter.

Body weight (without overcoat and shoes) will be measured at visit 0 (Screening), at visit 1 of each cycle, as part of the dose calculation, and at end of treatment visit, and will be recorded in the eCRF. If body weight is assessed 7 days or less (on the site weight) before the day of the planned dosing, this weight can be used and is the weight recorded in the eCRF.

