#### 7.1.1 Treatment Administration

Enapotamab vedotin will be administered as an i.v. infusion. Each patient's dose will be calculated based on the patient's weight rounded to the nearest kilogram, i.e., assigned cohort dose in mg/kg  $\times$  body weight in kg. For patients whose body mass index (BMI) is greater than 30 kg/m^2, the investigator should use a weight that, based on the patient's height, corresponds to a maximum BMI of 30.

The dose to be administered to the patient is calculated according to the following formula if BMI is greater than 30 kg/m^2:

$$Dose (mg) = x (mg/kg) * 30 (kg/m^2) * height (m) * height (m) \text{ (where } x \text{ denotes the dose level)}$$

Enapotamab vedotin will be administered over a minimum of 30 minutes and the infusion must be completed within 4 hours. The infusion is complete when the infusion line has been flushed with saline. For further details please refer to the IMP manual (Preparation and Administration of

Document Name: GCT1021-01 Protocol

Document Number: TMF-03326

Version: 11.0

---

enapotamab vedotin).

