**Footnotes to Trial Flowchart – Expansion**

- 1 If the patient shows PD, is to start new anti-cancer treatment or withdraws from treatment due to another reason the End of treatment visit should be performed as soon as possible after decision of withdrawal.
- 2 The visit windows relate to the day of the previous visit. Visit 1 of Cycle 2 and onwards should be performed 7 days ±3 days after Day 15/22 of the previous cycle.
- 3 Signs, symptoms and diagnosis occurring between Visit 0 and first infusion should be recorded as medical history (see Section 8.4 for details). SAEs should be reported as of the signing of the informed consent.
- 4 Body weight will be measured on the first dosing day in a cycle, as part of the dose calculation. If body weight is assessed ≤ 7 days before the first day of the planned dosing in a cycle, this weight can be used to calculate dose and is the weight recorded in the eCRF.
- 5 Temperature, blood pressure and heart rate as according to Section 8.4.8.
- 6 All patients will have a CT-scan with contrast of thorax, abdomen, and pelvis performed as part of the screening procedure. If a CT-scan has been performed within 28 days prior to visit CIV1 as part of standard procedure, it is acceptable as screening CT-scan for the trial. If there is suggestion of brain metastases/tumors, a CT-scan of the head will be performed before inclusion. Clinical measurement in case of superficial cutaneous lesions should be performed within 28 days prior to visit CIV1 as part of standard procedure. For further details on imaging please refer to Section 8.4.7.
- 7 Radiological assessments and clinical measurements of superficial cutaneous lesions are to be performed every 6 (1Q3W and Cohort 8 3Q4W) or 8 (Cohort 6 3Q4W) weeks (±7days) from C1D1 until disease progression. If treatment is discontinued prematurely, prior to detection of disease progression (e.g., due to an adverse event), every effort should be made that scans continue according to the protocol until disease progression, start of a new anti-cancer treatment, withdrawal of consent or death (see Section 8.4.7 for details).
- 8 To be completed as indicated to confirm response or new symptoms at the end of treatment visit or at the physician discretion.
- 9 TSH, T3 and T4 will only be measured at screening and on Visit 1 of every even cycle.

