 - with end date of IMP defined as min (date of last IMP administration + 20 days, last contact date, date of death, cut-off date) For 1Q3W schedule
 - with end date of IMP defined as min (date of last IMP administration + 27 days (if D1 of cycle) or 20 days (if D8 of cycle) or 13 days (if D15 of cycle), last contact date, date of death, cut-off date) For 3Q4W schedule
- Actual cumulative dose (mg): sum of all actual doses administered.
- Planned cumulative dose (mg) only used for calculation of relative dose intensity:
 Allocated dose level * weight in kg * number of cycles initiated for 1Q3W and allocated
 dose level * weight in kg * 3 * number of cycles initiated for 3Q4W. For subjects whose
 body mass index (BMI) is greater than 30 kg/m2, the formula should use a weight
 that, based on the subject's height, corresponds to a maximum BMI of 30. When a
 cycle is missed/skipped, this cycle is also included to count the number of cycles
 initiated.
- Dose intensity (mg/cycle): actual cumulative dose in mg divided by the number of cycles initiated.
- Relative dose intensity (%): 100 * ratio of actual cumulative dose and planned cumulative dose.
- Number of days in trial: max (last contact date, date of death) date of first IMP administration + 1.

Page 13 of 46

TPL N°: eTPL SA-02-01 Of SOP SA-02.08 TPL Effective Date: 31 Mar 2016 Genmab - GCT1021-01 Version: 4.0

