17.1 Extent of Exposure

For the expansion part, the number of doses received, the duration of exposure to enapotamab vedotin (days), the actual cumulative dose (mg), as well as the actual and relative dose intensities (continuous and in categories: >= 110%, 90% to < 110%, 70% to < 90%, 50% to < 70%, < 50%, missing) will be summarized by means of descriptive statistics using the safety set.

Version: 4.0

The duration of exposure to enapotamab vedotin (days) will also be presented by a Kaplan-Meier plot (without censoring).

Also, the number of subject days (total number of days in trial) will be presented by means of descriptive statistics for each dose/cohort group.

For the dose-escalation part, only the number of doses received, number of days in the trial and the duration of exposure will be presented as mentioned above.

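### SAP 4.6 builds planned dose on one unspecified body weight, while each cycle is dosed on a newly taken weight, so relative dose intensity mixes weight change with dose modification

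*Protocol*

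**What the plan says.** **Dosing.** Protocol 7.1.1 calculates each dose "based on the patient's weight rounded to the nearest kilogram, i.e., assigned cohort dose in mg/kg" times body weight. Above a BMI of 30, the weight corresponding to BMI 30 is used instead. Protocol 8.4.4 adds: "Body weight (without overcoat and shoes) will be measured at visit 0 (Screening), at visit 1 of each cycle". The expansion flowchart footnote says: "Body weight will be measured on the first dosing day in a cycle, as part of the dose calculation". A weight taken up to 7 days earlier may stand in. On 3Q4W, the three infusions of a cycle therefore share one weight.

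**Planned dose.** SAP 4.6 gives, for 1Q3W, "Allocated dose level * weight in kg * number of cycles initiated for 1Q3W"; for 3Q4W, the allocated "dose level * weight in kg * 3 * number of cycles initiated for 3Q4W". It repeats the BMI cap and counts missed or skipped cycles as initiated. It does not say which visit's weight is meant.

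**Use.** In the same section, actual cumulative dose is the total mg given, and RDI is 100 times actual over planned. Planned dose has no other use. SAP 17.1 summarises RDI for the expansion part only, as a continuous variable and in bands with cuts at 110%, 90%, 70% and 50%; the bands include "90% to < 110%, 70% to < 90%, 50% to < 70" per cent.

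**The concern.** The numerator of RDI follows the patient's current weight, because every mg dose does. The denominator has a single weight multiplied by a number of cycles. The two agree only if weight is constant or if the single weight happens to equal the average dosing weight. Otherwise a patient given every mg/kg as assigned does not read 100%, and a patient with a real reduction reads higher or lower than the reduction warrants.

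RDI is the output that shows how much of the assigned dose was delivered. SAP section 4 places the 1.8 and 2.2 mg/kg groups of Cohort 2 side by side, and tolerability is the stated reason for the lower-dose group. If weight change or time on treatment differs between such groups, the RDI comparison is distorted. The unspecified weight is also a fault in itself: two programmers could obtain different RDI values from the same data.

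**Working it through.** The documents give no RDI value and no weight data, so there is no stated figure to reproduce. The check applies the SAP formula to assumed weight paths.

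**Inputs from the documents:** dosing on the weight of each cycle, rounded to the kilogram and capped at BMI 30 (Protocol 7.1.1, 8.4.4, expansion flowchart footnote); RDI and planned dose (SAP 4.6); bands (SAP 17.1); dose levels 2.2 mg/kg 1Q3W and 1.0 mg/kg 3Q4W (SAP 4.5.2).

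**Assumptions:** 70 kg at cycle 1, 8 cycles, linear change of 5% to 20%, or a step loss from cycle 2. The change from 2.2 to 1.8 mg/kg from cycle 4 is an arithmetic illustration only.

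**Formula.** Let D be the allocated mg/kg, dᵢ the mg/kg given in cycle i, wᵢ the dosing weight in cycle i, W the single weight, n the number of cycles and k the infusions per cycle (1 or 3).

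- As the SAP is written: RDI = 100 × Σ k dᵢ wᵢ / (k D W n)
- With a per-cycle denominator: RDI = 100 × Σ k dᵢ wᵢ / (k D Σ wᵢ)
- Ratio of the first to the second: (Σ wᵢ / n) / W, the mean dosing weight over the single weight. k cancels, so both schedules behave alike.

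**By hand.**

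- Full dosing, 10% linear loss: mean weight = (70 + 63)/2 = 66.5 kg. With W = 70, RDI = 66.5/70 = 95.0%. With W = 63, RDI = 66.5/63 = 105.6%.
- Full dosing, 15% loss from cycle 2: 59.5 kg, dosed as 60. RDI = (70 + 7 × 60)/(8 × 70) = 490/560 = 87.5%.
- Reduction, constant weight: (3 × 2.2 + 5 × 1.8)/(8 × 2.2) = 15.6/17.6 = 88.6%.
- Reduction, 5% linear gain (70 to 73.5 kg): the first three weights sum to 211.5 and the last five to 362.5. Actual = 2.2 × 211.5 + 1.8 × 362.5 = 1117.8 mg. Planned with W = 70 is 2.2 × 70 × 8 = 1232 mg, giving 90.7%. Planned per cycle is 2.2 × 574 = 1262.8 mg, giving 88.5%.

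**RDI (%) by choice of W:**

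| Path | W = cycle 1 | W = last | W = mean | Per-cycle sum |
|---|---|---|---|---|
| Full dose, constant weight | 100.0 | 100.0 | 100.0 | 100.0 |
| Full dose, 5% linear loss | 97.5 | 102.6 | 100.0 | 100.0 |
| Full dose, 10% linear loss | 95.0 | 105.6 | 100.0 | 100.0 |
| Full dose, 20% linear loss | 90.0 | 112.5 | 100.0 | 100.0 |
| Full dose, 15% loss from cycle 2 | 87.5 | 102.9 | 100.7 | 100.0 |
| Full dose, 10% linear gain | 105.0 | 95.5 | 100.0 | 100.0 |
| Reduced, constant weight | 88.6 | 88.6 | 88.6 | 88.6 |
| Reduced, 5% linear gain | 90.7 | 86.4 | 88.5 | 88.5 |
| Reduced, 10% linear gain | 92.8 | 84.4 | 88.4 | 88.4 |
| Reduced, 20% linear gain | 97.0 | 80.8 | 88.2 | 88.2 |

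The full-dose linear-loss rows are identical for 1.0 mg/kg 3Q4W. The 100.7 arises because doses are rounded to the kilogram and the mean weight is not.

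**BMI cap.** At 1.70 m the cap is 30 × 1.70² = 86.7 kg. A fall from 100 to 90 kg leaves the dosing weight unchanged, and RDI is about 100% under every choice of W.

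**The case against.** The strongest reply is that SAP 4.6 is ambiguous rather than wrong. It names no visit, and because it repeats the BMI cap used for dosing, its weight term could be shorthand for the dosing weight. That is possible, and it limits what can be said about direction. It does not rescue the formula: a weight multiplied by a count of cycles is not a sum over cycle weights, and of the single choices only the mean comes close to the right answer.

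The second reply is that the bands absorb most of the effect. For weight loss under a cycle 1 denominator this stands: a linear loss of up to 20% still reads at least 90% in a fully dosed patient, and crossing that cut through loss alone needs an average loss above 10%. The continuous summary moves regardless, and a patient already just below 90% can be carried over the cut by a small gain.

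The third reply is that reach is small. This also stands. RDI is descriptive and reported for the expansion part only. Dose reductions appear independently in the tables of adverse events leading to reduction and in the exposure listing, and body weight over time is summarised (SAP 17.2, 17.6.2, 20.3).

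A reader might infer more than the documents support:

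- That weight loss necessarily reads as dose reduction and gain hides one. This needs the baseline or cycle 1 weight, which the SAP does not specify.
- That SAP 17.6.1 expects 10% weight changes. It only sets 10% as a limit for flagging a value as clinically notable.
- That the distortion differs by tumour type. No weight data by cohort are given.

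**Conclusion.** The point holds in a limited form. Taken literally, SAP 4.6 yields an RDI equal to the true value times the mean dosing weight over one unspecified weight.

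Under a baseline or cycle 1 weight, which is the natural reading, the shift for linear weight change is about half the percentage change: 2.5 points for 5% and 5 points for 10% in a fully dosed patient. In the illustration, a 5% gain moves a true reduction from the band below 90% to the band above it. Under the last weight the direction reverses. Under the mean weight the effect is nearly gone.

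These sizes rest on assumed weight paths. There is no effect while BMI stays above 30. DLTs, MTD, response, PFS, OS and the AE-based dose-reduction tables are untouched. It is worth correcting because RDI is otherwise not interpretable as dose delivery, but no primary conclusion depends on it.

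**What to change.** In SAP 4.6, define planned cumulative dose as the sum over initiated cycles of: allocated mg/kg × the weight used for that cycle's dose calculation (rounded to the kilogram and capped at BMI 30, as in Protocol 7.1.1) × the infusions planned in that cycle. Missed or skipped cycles stay in the count, as now, but have no dosing weight of their own, so state that the last recorded dosing weight is carried forward for them. Leave the RDI ratio and the bands unchanged. In the calculations above, this gives 100.0% for full dosing on every path and keeps the reduced-dose case at 88.2% to 88.6%.

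The data exist: Protocol 8.4.4 records the cycle weights in the eCRF, and recording stopped only with Amendment 10 (30 June 2021), after the 22 March 2021 cut-off.

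The programming is small, but the change is after the fact. The SAP addendum says data to the cut-off have already been reported in the CSR, and its output list does not repeat the exposure table. It does rerun all derived-dataset programs on the whole database, so the choice is between rerunning the exposure table and adding a footnote in the CSR addendum that names the weight used and its effect on RDI.

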#### **8.4.5 Physical Examination**

A complete general physical examination will be done at the screening and C1D1 visit including peripheral neuropathy assessment, such as checking of tendon reflexes, muscle strength and tone, sensitivity, co-ordination and balance. A baseline visual acuity assessment will be performed at the screening visit using the Snellen chart.

At subsequent visits (or as clinically indicated), limited symptom-directed physical examinations should be performed and the outcome of the physical examination must be recorded in the eCRF. Changes from baseline abnormalities should be recorded in patient's notes. New or worsened clinically significant abnormalities should be recorded as AEs on the AE form. The peripheral neuropathy assessment should also be performed at the End of Treatment visit.

An unscheduled general physical examination should always be considered, if a significant clinical finding is observed.

#### **8.4.6 Electrocardiogram**

The electrocardiograms (ECGs) will be recorded digitally at the sites by using the standard 12 leads. ECGs will be performed in accordance with the ECG manual issued by the vendor and as described below.

The digital ECGs will be transmitted from the sites electronically to a central laboratory for a treatment blinded measurement of the cardiac intervals and morphologic assessment by a central cardiologist.

An overall interpretation of the ECGs must be performed by the investigator (the investigator may delegate this task to a cardiologist or other qualified staff member, if applicable) before each dosing for use of treatment decision (with the exception of evaluation of patient eligibility which must be

Document Name: GCT1021-01 Protocol

Document Number: TMF-03326

Version: 11.0

evaluated based on the central ECG reading). The investigator ECG interpretation must be done using the paper ECG reading from the ECG machine by signing and dating the print out. In case of discrepancy between central and the investigator ECG readings, the central reading will be used for trial analysis purposes. For the ECG recordings, the patients must be resting and in a horizontal or half laid-back position for at least 10 minutes (the position should not change for following ECGs). Any irregularity observed or occurring during the ECGs (e.g., vomiting, cough) should either induce a repeat of the ECG or be annotated on the eCRF with the description and time of the occurrence.

Date of the ECG and the overall interpretation of the ECGs will be recorded in the eCRF.

ECGs will be taken as single or triplicate ECGs according to the tables below.

#### 8.4.6.1 ECG Assessment

**Table 17. ECG Assessments Dose Escalation, 1Q3W**

Treatment Cycle	Screening	Cycles 1 and 3				Cycle 2, 4-16	Cycle 17 to PD	End of treatment	Unscheduled
Visit Number	0	1	3	4	5	1	1	-	1-X
Day/Week	≤ 21 days prior to Visit C1V1	1d	4d	8d	15d	1d	1d	-	-
Before infusion (on infusion days)	1	3	3	3	3	3	1	1	1 a
End of infusion (+15 minutes)		3							
End of infusion + 2 hours (± 15 minutes)		3							
End of infusion + 5 hours (± 30 minutes)		3							

1 = Single ECG assessment; 3= Triplicate ECG assessments

aECG assessed if relevant

**Table 18. ECG Assessments Dose Escalation, 3Q4W**

Treatment Cycle	Screening	Cycles 1 and 3				Cycle 2, 4-12	Cycle 13 to PD	End of treatment	Unschedule d
Visit Number	0	1	3	5	6	1	1	-	1-X
Day	≤21 days prior to Visit C1V1	1d	15 d	17 d	22d	1d	1d	-	-
Before infusion (on infusion days)	1	3	3	3	3	3	1	1	1 a
End of infusion (+15 minutes)			3						
End of infusion + 2 hours (± 15 min)			3						
End of infusion + 5 hours (± 30 min)			3						

1 = Single ECG assessment; 3 = Triplicate ECG assessments

aECG assessed if relevant

Document Name: GCT1021-01 Protocol

Document Number: TMF-03326

Version: 11.0

**Table 19. ECG Assessments Expansion Part**

Treatment Cycle		Screening	Cycle 1 to PD	End of Treatment	Unscheduled
1Q3W	Visit	≤21 days prior to Visit C1V1	1	-	1-X
	Day		1d	-	-
Before infusion (on infusion days)		1	3	1	1 a

Treatment Cycle		Screening	Cycle 1 to PD	End of Treatment	Unscheduled
3Q4W	Visit	≤21 days prior to Visit C1V1	1	-	1-X
	Day		1d	-	
Before infusion (on infusion days)		1	3	1	1 a

1 = Single ECG assessment; 3 = Triplicate ECG assessments

aECG assessed if relevant

#### 8.4.7 Imaging/Computed Tomography

All patients will have a CT-scan with contrast of thorax, abdomen and pelvis performed during screening. If there is suspicion of brain metastases/tumors, a CT-scan of the head will be performed before inclusion. For patients with stable brain metastases enrolled in the expansion part, the CT-scan must include the head and neck.

For patients with superficial cutaneous lesions that are not measurable by a CT-scan, measurement using calipers can be performed, using photographs as documentation.

All sites of metastatic disease should be reported at baseline and followed throughout the trial. Up to 5 target lesions (maximum two per organ) will be defined at screening. A lesion from which a fresh biopsy has been taken during the trial cannot be a target lesion.

Baseline imaging assessments will be performed during the screening period. Any imaging assessments already completed for regular radiographic evaluation of the patient's cancer can be considered as the baseline images for this trial, as long as they are of sufficient diagnostic quality and have been obtained ≤ 28 days prior to C1D1.

Post-baseline scans will be performed every 6 weeks (1Q3W and Cohort 8 3Q4W) or 8 weeks (Cohort 6 3Q4W) (±7 days) from C1D1 until investigator assessed disease progression according to RECIST v1.1. Time points for radiographic evaluation should be calendar based and do not depend on cycle visits i.e. radiological evaluation should be performed regardless of IMP administration delays. For patients who permanently discontinue IMP for other reasons than disease progression (e.g., adverse events), every effort should be made to continue on-trial radiological evaluation according to protocol until disease progression, start of a new anti-cancer treatment, withdrawal of consent or death (see [Table 11](#)).

Document Name: GCT1021-01 Protocol

Document Number: TMF-03326

Version: 11.0

---

If reduction of target lesions  $\geq 30\%$  in size is observed a repeat CT-scan will be performed after 4 (in particular for the 3Q4W-arm) to 6 weeks (in particular for the 1Q3W-arm) to confirm the response.

Unscheduled imaging may be performed at the investigators discretion to confirm response (intervals should not be shorter than 4 weeks). In case of suspicion of disease progression on the basis of clinical or laboratory findings, imaging should be performed as soon as possible before the next scheduled evaluation. In this case the investigator must choose the imaging technology based on the clinical indication. For patients in the expansion part, all supplemental images must be submitted for central reading.

MRI can be performed instead of CT-scan if the patient is allergic to iodine contrast or at the discretion of the investigator, after approval of the sponsor.

Localized CT with contrast or MRI (with or without contrast; for sarcomas with contrast) must be acquired for assessment of lesions of the skeleton/extremities and head and neck if not visible on other images. At the discretion of the investigators, combined PET/CT (e.g., FDG-PET) may be performed for tumor assessments as per RECIST 1.1, but only if the CT portion is of similar diagnostic quality to CT alone. Chest x-rays and ultrasound should not be used to measure tumor lesions.

The same imaging modality and ideally the same scanner should be used throughout the trial to optimize the reproducibility of the assessment and preserve the accuracy of the assessment of response or progression.

In the dose escalation part the reading of the scans will be done by a local radiologist. Sites should attempt to maintain the same radiologist throughout the trial. The overall interpretation of the evaluation shall be recorded in the eCRF and a copy of the evaluation reports should be kept in the patient's file.

In the expansion part the scans will be read by the local radiologist and subsequently sent for central reading and archiving.

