### **6.3.1 Criteria for Patient Withdrawal from Treatment**

Patients can be withdrawn from treatment for the following reasons:

- Unacceptable toxicity reported as AEs (see Section 7.3 for specifications, exceptions and dose modifications)
- Pregnancy
- Withdrawal of consent
- Investigator or sponsor decision due to individual patient safety issues not covered by other withdrawal criteria
- Disease progression according to RECIST 1.1 or clinical disease progression

Patients should, whenever possible, irrespective of the reason for withdrawal, be examined as soon as possible at the end of treatment visit.

Patients being withdrawn from treatment for any reason will have a safety follow-up visit 30 days after last treatment as well as follow-up contacts every 12 weeks after last dose.

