**Table 26. Definition of Response (RECIST Criteria v1.1)**

	Category	Criteria
Based on target lesions	Complete Response (CR)	Disappearance of all target lesions. Any pathological lymph nodes must have reduction in short axis to < 10 mm.
	Partial Response (PR)	≥ 30% decrease in the sum of the LD of target lesions, taking as reference the baseline sum LD.
	Stable Disease (SD)	Neither sufficient shrinkage to qualify for PR nor sufficient increase to qualify for PD, taking as reference the smallest sum of LDs since the treatment started.
	Progressive Disease (PD)	≥ 20% increase in the sum of the LDs of target lesions, taking as reference the smallest sum of the LDs recorded since the treatment started or the appearance of one or more new lesions.
Based on non-target lesions	CR	Disappearance of all non-target lesions and normalization of tumor marker level. All lymph nodes must be non-pathological in size (< 10 mm short axis).
	SD	Persistence of one or more non-target lesion(s) or/and maintenance of tumor marker level above the normal limits.
	PD	Appearance of one or more new lesions and/or unequivocal progression of existing non-target lesions.

Evaluation of best overall response (RECIST Criteria v1.1)

The best overall response is the best response recorded from the start of the treatment until disease progression/recurrence (taking as reference for PD the smallest measurements recorded since the treatment started).

Patients with a global deterioration of health status requiring discontinuation of treatment without objective evidence of PD at that time should be classified as having “symptomatic deterioration”. Every effort should be made to document the objective progression even after discontinuation of treatment.

Document Name: GCT1021-01 Protocol

Document Number: TMF-03326

Version: 11.0

---

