15.1.4 Progression-Free Survival according to RECIST 1.1

PFS is defined as the number of days from the date of first IMP administration to first PD or death whichever occurs first.

PFS will be derived for all subjects and presented graphically as well as summarized using survival analysis methods:

- Kaplan-Meier curves
- Kaplan-Meier curves by subgroups defined for cohorts 2 and 8 and for cohort 6 as mentioned in section 4.4
- Kaplan-Meier estimates.
- Kaplan-Meier estimates by subgroups defined for cohorts 2 and 8 and for cohort 6 as mentioned in section 4.4.

PFS will be censored in accordance with Table A in Appendix 3 in the FDA Guidance for Industry "Clinical Trial Endpoints for the Approval of Cancer Drugs and Biologics (2007)".In summary, PFS will be censored if no event (progression or death) is observed before the first of (i) the analysis cut-off date, and (ii) the date when a new anti-cancer therapy is started. The censoring date will be the date of the last adequate tumor assessment prior to cut-off/start of new anti-cancer therapy. In case of an event after 2 or more missed scans, censoring will be done at last adequate tumor assessment date before the missed scans (Censoring rule based on FDA guideline). Two scans are considered missing if no evaluable response result (CR, PR, SD or PD) is available within a period of 98 days (6+1 weeks times 2) for 1Q3W dose schedule and a period of 126 days (8+1 weeks times 2) for 3Q4W dose schedule.

[figure not shown]

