15.1.8 Events over Time - Expansion Part

Swimlane plots in which each lane documents the individual subject experience on a trial over time will be created for all confirmed responder subjects. The plots will include ontreatment, off-treatment periods, response according to RECIST 1.1 (investigator assessment), clinical progression and NLCB.

The no longer clinically benefitting (NLCB) reporting metric is defined as the date and the specific reason(s) a therapy was ultimately discontinued (end of treatment visit date).

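### Clinical progression can end treatment but is not a PFS or DoR event, so some of these patients are censored informatively at their last scan, and no sensitivity analysis is planned

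*Protocol*

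**What the plan says.** - **Stopping treatment.** Protocol 6.3.1 gives as one reason "Disease progression according to RECIST 1.1 or clinical disease progression".
- **Scanning.** Protocol 8.4.7 schedules scans by calendar "until investigator assessed disease progression according to RECIST v1.1". It then says: "For patients who permanently discontinue IMP for other reasons than disease progression (e.g., adverse events), every effort should be made to continue" radiological evaluation. The same section adds: "In case of suspicion of disease progression on the basis of clinical or laboratory findings, imaging should be performed as soon as possible". Table 11 footnote 7 reads: "If treatment is discontinued prematurely, prior to detection of disease progression (e.g., due to an adverse event), every effort should be made that scans continue".
- **Deterioration without objective progression.** The text under Table 26 in Protocol 10.4 says: "Every effort should be made to document the objective progression even after discontinuation of treatment".
- **PFS.** SAP 15.1.4 counts first PD or death. "PFS will be censored if no event (progression or death) is observed before the first of" the analysis cut-off and the start of new anti-cancer therapy; the censoring date is the last adequate assessment before that. An event after two or more missed scans is also censored back, with a window of 98 days for 1Q3W and 126 days for 3Q4W.
- **DoR.** SAP 15.1.6 uses the same rules.
- **Use of clinical progression.** SAP 15.1.8 shows "clinical progression and NLCB" in swimlane plots of confirmed responders. No PFS or DoR analysis uses it.

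**The concern.** Patients judged to be progressing clinically have a poor outlook. If they leave the PFS risk set at a scan that precedes that judgement, Kaplan-Meier treats them as having the same future risk as patients who are still progression-free. The error goes one way: PFS looks longer. There is no control arm in which a similar error could offset it.

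The scan wording makes this more likely. Protocol 6.3.1 puts RECIST and clinical progression together under disease progression. A site that carries that usage into 8.4.7 could conclude that the request to keep scanning does not apply after a clinical stop, whereas 10.4 asks for objective documentation in that very situation.

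PFS and DoR are secondary endpoints, and the SAP plans nothing that would show a reader how much of either result depends on this.

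**Working it through.** **1. The plan's own figures.** The missed-scan windows reproduce: (6+1) × 2 × 7 = 98 days and (8+1) × 2 × 7 = 126 days.

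**2. What happens after a clinical stop (SAP 15.1.4).**
- RECIST PD or death before new therapy and before two missed scans: counted as an event.
- New therapy first: censored at the last adequate scan. Complete scanning up to that point does not prevent this.
- No timely scan or death: censored at the last adequate scan.

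The size of the bias therefore depends on f, the share of progressors who progress clinically, and d, the share of those with a later event that counts. The documents give neither, nor an expected median PFS.

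**3. Simulation.** Assumptions: exponential progression times with median 3, 4 or 6 months; scans every 42 days ±7; 40,000 patients per scenario; follow-up cut at 2 years. RECIST progression is dated at the next scan. Clinical progressors with a later counted event are dated at the next scan; the others are censored at their last scan (day 1 if none). Reference analysis: clinical progression is an event on its own date.

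Rise in 6-month Kaplan-Meier PFS, in percentage points (range over the three medians):

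| f | d = 0 (none documented) | d = 0.5 | d = 1 (all documented) |
|---|---|---|---|
| 5% | 1.5-1.7 | 0.8-0.9 | 0.1-0.2 |
| 10% | 3.2-3.4 | 1.7-1.8 | 0.3 |
| 20% | 6.7-7.2 | 3.3-3.7 | 0.5-0.7 |
| 30% | 10.7-11.4 | 5.3-5.7 | 0.8-0.9 |

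Example with median 3 months and f = 20%: 27.5% becomes 34.1% if none is documented, 27.6% becomes 30.9% if half are, and 27.6% becomes 28.1% if all are.

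**4. Hand check of one cell** (median 3 months = 91.3 days, f = 0.2, d = 0, no scan window):
- Progression probability per scan interval: p = 1 − 2^(−42/91.3) = 0.273.
- Reference at day 183, after four scans: 0.8 × (1 − 0.273)^4 + 0.2 × 2^(−183/91.3) = 0.8 × 0.279 + 0.2 × 0.249 = 0.273.
- SAP rule: the hazard at each scan is 0.8p / (1 − 0.2p) = 0.218/0.945 = 0.231, so PFS = (1 − 0.231)^4 = 0.350.
- Difference: about 7.6 points, against 6.7 in the simulation. The ±7-day window accounts for the gap.

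**5. Limits.** The difference in median PFS runs from 0 to 1.7 months, but it jumps with the scan grid, so the 6-month rate is the steadier measure. DoR was not simulated.

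**The case against.** A reader might infer that every clinical progressor drops out of scanning and is censored. The documents do not support that. Protocol 8.4.7 runs scans to RECIST progression, not to the end of treatment, and asks for prompt imaging on clinical suspicion. Footnote 7 covers stopping before progression is detected. Protocol 10.4 asks for objective progression to be documented after stopping. A timely PD or death counts. All of this stands, and if it works in practice the bias is close to zero.

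Two routes remain open. A prompt scan may fall short of RECIST progression in a patient who still stops on clinical grounds. New anti-cancer therapy ends the request for scans and censors PFS however good compliance has been.

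It is also fair to say that RECIST-only PFS with the FDA Table A censoring is a legitimate pre-specified endpoint, that counting a clinical judgement as an event defines a different one, and that such a judgement is subjective. That is a reason to keep the RECIST analysis as the main one, not a reason to omit a sensitivity analysis.

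Some information is already planned: SAP 5.1 summarises the reasons for stopping, the swimlane plots cover the confirmed responders who make up the DoR population, and OS (SAP 15.2) is not censored for skipped visits or new therapy. None of this shows the effect on the PFS or DoR estimate.

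The stakes are modest. The primary objective is MTD and safety, the formal expansion tests are on response rate, PFS is descriptive, and development has been discontinued.

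**Conclusion.** The point holds for a subset: patients who stop for clinical progression and then start new therapy, or have no RECIST PD or death before two missed scans. For them the censoring is informative and PFS is biased upward. DoR shares the rules and so the direction, but its size is unknown.

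At f = 5-30%, the overstatement of 6-month PFS is about 0-1 point if all are later documented, 1-5.5 if half are, and 1.5-11 if none is. These figures rest on assumed shares, medians and exponential progression. A reader might take the upper end as this trial's bias; it would require that the imaging and documentation requests were never met and that no timely death occurred, which the documents give no reason to assume.

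The 8.4.7 phrase is an ambiguity to be reconciled with 10.4, not proof that these patients went unscanned. The firm gap is the missing sensitivity analysis.

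**What to change.** 1. **SAP 15.1.4 and 15.1.6, and the PFS rerun in SAP addendum 3.2.** Add a sensitivity analysis of PFS and DoR in which clinical progression, given as the reason for stopping treatment, is an event on that date. Show it beside the unchanged RECIST-only result.
2. **Report the count.** Give the number of patients per group who were censored for PFS after stopping for clinical progression. This shows directly whether the issue matters here.
3. **Protocol 8.4.7.** Reconcile the phrase on reasons other than disease progression with 10.4. This clarifies the record only: enrolment is complete, the trial has ended according to the SAP addendum, and missed scans cannot be recovered.

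Cost: one extra table and curve for each endpoint. The reason for stopping is already summarised (SAP 5.1), and the stop date with its reason is defined for the swimlane plots (SAP 15.1.8). The documents do not show that a separate date of clinical progression exists for every patient, so the SAP should name the date to be used. Because clinical progression is subjective, the RECIST analysis stays the main one.
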